# 8.5 Dose Limiting Toxicities

Adverse events will be graded according to NCI CTCAE, version 4.0, with a DLT being defined as an AE assessed as having a suspected or unknown relationship to the study drug (MOR03087, POM, or LEN) and meeting one of the following criteria:

- Non-hematologic DLT:
  - o Liver

Any grade 3 AST/ALT that does not resolve to grade 1 within 14 days or any grade 4 elevation in liver function tests (AST/ALT)

- Gastrointestinal
  - $\geq$  Grade 3 vomiting or nausea despite the use of standard antiemetics

Sponsor: MorphoSys AG

- $\geq$  Grade 3 diarrhea or constipation despite the use of optimal treatment
- All other events
  - ≥ Grade 3 (excluding hypersensitivity reactions and fatigue)
- Hematologic DLT:
  - Grade 4 thrombocytopenia that requires more than one platelet transfusion and does not resolve to grade 2 or less within 14 days
  - Grade 4 neutropenia that does not resolve to grade 2 or less within 14 days
  - Or any other grade 4 hematologic toxicities that do not resolve to grade 2 or less within 14 days and that are considered clinically relevant by the investigator
- Any AE that delays treatment with study drug for more than 14 days

In addition, any event will only qualify as a DLT if a worsening of the event from baseline of at least 2 CTCAE Grades occurs.

The DLTs for the POM combination cohorts are specified as above except for the hematological DLTs which are as follows:

- Hematologic DLT:
  - Grade 4 neutropenia for > 7 days
  - Febrile neutropenia (ANC <1000/mm³ with a single temperature of >38.3°C or a sustained temperature of  $\geq$  38°C for more than 1 hour)
  - o Thrombocytopenia
    - Platelet count  $< 25,000/\mu$ L that requires more than one platelet transfusion or
    - Platelet count  $\ge 25,000/\mu L$  to  $< 50,000/\mu L$  with significant bleeding (defined as need for hospitalization and/or platelet transfusion)
  - Or any other grade 4 hematologic toxicities that do not resolve to grade 2 or less within 14 days and that are considered clinically relevant by the investigator

The DLTs for the LEN combination cohorts are specified as above except for the hematological DLTs which are as follows:

- Hematologic DLT:
  - Grade 4 neutropenia for > 7 days
  - Febrile neutropenia (ANC <1000/mm³ with a single temperature of >38.3 °C or a sustained temperature of  $\geq$  38 °C for more than 1 hour)
  - o Thrombocytopenia

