3.2 Selection of Study Population

This is a phase I/IIa study in adult subjects with relapsed or refractory MM as monotherapy and in combination with standard therapy. Key inclusion criteria identified in the protocol are

1. Male or female subjects ≥ 18 years of age
2. Presence of serum M-protein ≥ 0.5 g per 100 mL (≥ 5 g/L) and/or urine M-protein ≥ 200 mg per 24-hour period
3. Life expectancy of > 3 months
4. Karnofsky performance status $\geq 60\%$
5. Absolute neutrophil count ≥ 1.0 (1,000/mm³)
6. Total bilirubin $\leq 2 \times$ the upper limit of normal (ULN)
7. Alanine transaminase and aspartate aminotransferase $\leq 2.5 \times$ ULN
8. Hemoglobin ≥ 8 g/dL

Additional key inclusion criteria are defined differently for monotherapy and different combination therapies:

Additional Key Inclusion Criteria for Treatment With MOR03087 With/Without Dexamethasone

1. Documented diagnosis of MM; specifically, relapsed or refractory MM defined as:
 - Failure of at least 2 previous therapies; previous therapies must include an immunomodulatory agent and a proteasome inhibitor (either together or as part of different therapies)
 - All subjects must have documented progression during or after their last prior therapy for MM
2. Creatinine clearance ≥ 30 mL/min (calculated using the Cockcroft-Gault equation)
3. Platelets:
 - $\geq 80 \times 10^9/L$, without previous transfusion within the last 4 weeks before first study drug administration

- $\geq 50 \times 10^9/L$ (for dose levels ≥ 4 mg/kg with or without DEX). Subjects are not allowed to have received platelet transfusion within the last 4 weeks before study drug administration.

Additional Key Inclusion Criteria for the Treatment With MOR03087, Dexamethasone and Lenalidomide

1. Documented diagnosis of MM; specifically, relapsed or refractory MM defined as:
 - Received at least 1 previous therapy
 - All subjects must have documented progression during or after their last prior therapy for MM
2. Creatinine clearance ≥ 50 mL/min (calculated using the Cockcroft-Gault equation)
3. Platelets:
 - $\geq 75 \times 10^9/L$ for subjects in whom $< 50\%$ of bone marrow nucleated cells are plasma cells
 - $\geq 30 \times 10^9/L$ for subjects in whom $\geq 50\%$ of bone marrow nucleated cells are plasma cells.

Additional Key Inclusion Criteria for the Treatment With MOR03087, Dexamethasone and Pomalidomide

1. Documented diagnosis of MM; specifically, relapsed and refractory MM defined as:

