Categorical, qualitative variable summaries will include the frequency and percentage of subjects who are in a particular category. Unless otherwise stated the calculation of proportions will be based on the number of subjects of the analysis set of interest. Therefore counts of missing observations will be included in the denominator and presented as a separate category. [REDACTED]

The last pre administration observation will be used as the baseline value for calculating post administration changes from baseline. Thus baseline will be Cycle 1 Day 1 in case there is a value available (not missing) and screening otherwise.

All data obtained on the electronic case report for (eCRF) and entered into the database will be provided in separate data listings showing individual subject values. The planning and reporting of statistical analyses will be carried out as described in the Premier Research Biostatistics standard operating procedures.

Any subject who withdraws from the study will be analyzed with the data available. Imputation of missing values will not be performed.

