10.2 Adverse Events

All TEAEs and SAEs will be coded using MedDRA (MedDRA Version 20.1, and updated to the newest version 23.0 for the follow-up analyses).

The body systems 'Blood and lymphatic system disorders' and 'Investigations' will be combined for the purpose of analysis. Moreover, all preferred terms from those two body systems that are subsequently listed in the same row will be combined:

- Red blood cell count decreased / Haemoglobin decreased / Haematocrit decreased / Mean cell volume decreased / Anaemia
- Fibrin D dimer increased / International normalised ratio increased / Prothrombin time shortened / Coagulopathy
- Eosinophil count increased / Eosinophilia
- Blood fibrinogen increased / Hyperfibrinogenaemia
- White blood cell count increased / Leukocytosis
- White blood cell count decreased / Leukopenia
- Lymphocyte count decreased / Natural killer cell count decreased / CD4 lymphocytes decreased / B-lymphocyte count decreased / Lymphopenia
- Monocyte count decreased / Monocytopenia
- Neutrophil count decreased / Neutropenia
- Neutrophil count increased / Neutrophilia
- Plasma cells increased / Plasmacytosis
- Platelet count decreased / Thrombocytopenia

TEAEs are defined as AEs occurring or worsening after the start (date and time) of the first study treatment (any IMP) and up to 28 days after the last study treatment including all treatment cycles (treatment emergent period). However, AEs occurring or worsening later than 28 days after the last treatment with study drug are defined as treatment emergent if these are considered to be related to the study drug.

If the start date and time of an AE are partially or completely missing, the AE will be assumed to be treatment-emergent if it cannot be definitely shown that the AE did not occur or worsen during the treatment-emergent period (worst case approach). Missing dates and times will not be replaced.

Thus, the following approach will be taken:

- If the start time of an AE is missing but the start date is complete, an AE will only be excluded from TEAEs if the start day is before the day of first treatment or the start day is after the end day of the treatment-emergent period.
- If the start time and day are missing but the start month is complete, an AE will only be excluded from TEAEs if the start month is before the month of first treatment or the start

month is after the end month of the treatment-emergent period or if stop date/time is before start of first treatment.

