10.3 Clinical Laboratory Evaluations

Safety laboratory data (hematology, serum chemistry, endocrinology, coagulation, urinalysis) will be analyzed by the respective local laboratories of each involved site.

The analysis of safety laboratory parameters will be presented separated into blood parameters (hematology, serum chemistry, endocrinology, coagulation) and urine parameters (urinalysis). All data will be listed.

The blood parameters will be transformed to SI values based on SI units to make laboratory parameters comparable between different local laboratories. The relevant reference ranges supplied by each laboratory will also be transformed to SI reference ranges for each laboratory.

Descriptive summaries of actual (absolute) values and changes from baseline values will be presented for all blood parameters.

Creatinine clearance will be calculated according to the Cockcroft-Gault formula and will be included in descriptive summaries of actual (absolute) values and changes from baseline.

Each abnormal value will be flagged to show whether it is a value below or above the reference range. For the assessment of laboratory variables, 5 categories will be used that take into account

the investigator's assessment of clinical relevance: 'clinically relevant, above', 'non-clinically relevant, above', 'within', 'non-clinically relevant, below', 'clinically relevant, below'.

The assessment of laboratory variables will be tabulated by time point for each clinical laboratory analyte (frequency tables).

If NCI-CTCAE grades are available for a clinical laboratory analyte, these will be derived according to NCI-CTCAE version 4.0 and used to present additional frequency based on NCI-CTCAE grades.

For hematology parameters, shifts in assessments from baseline to worst-post baseline will be presented based on classifications relative to the laboratory reference ranges (low/normal/high) for hematology parameters where NCI-CTCAE grades are not defined. If a subject experiences both "Low" and "High" assessments in the course of the trial, the worst post-baseline will be defined as "Low and High".

If NCI-CTCAE grades are available for a hematology parameter, frequency, shift and summary tables based on grades will be created as follows:

- Incidence of subjects with worst post-baseline grade. Each subject will be counted only for the worst grade
- Shift tables to compare baseline to the worst post-baseline value using CTCAE grades

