- Summary of time to onset to worst post-baseline grade (defined as the time from treatment start to first occurrence of worst post-baseline grade): this table will present summary statistics over all grades, but only patients with a worst post-baseline grade will be included.

A separate listing will be prepared to list the time course of a laboratory parameter for a subject with any abnormal, clinically significant laboratory value (for all laboratory values irrespectively of whether NCI-CTCAE grades are available).

The investigator's assessment of categorical urinalysis variables ('normal', 'abnormal, not clinically significant', 'abnormal clinically significant') will be tabulated by time point for each urine parameter (frequency tables).

Additionally, for each of these urine parameters, shifts in assessments from baseline to Cycle 2 Day 1 and to EOS will be presented for combined data.

For all shift tables, baseline percentage will be based on the number of patients in the analysis set (N). Percentage for worst post-baseline value will be based on Baseline n for the baseline category the percentage refers to.

Laboratory values that are outside the reference range will also be flagged in the data listings, along with corresponding reference ranges.

Results of unscheduled laboratory evaluations, laboratory data of the emergency laboratory, results of urine microscopy (if available), results of the pregnancy test and screening serology results will only be included in listings.

In general, laboratory summaries except for the tables analyzing the hematology parameters (worst post-baseline assessments/grades) as described above will only include time points of Cycle 1+2 and EOS visit. For the tables analyzing the hematological parameters, all available time points will be included when deriving worst assessment/worst grade.

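### The SAP's hematology time-to-worst-grade table does not require the grade to exceed baseline, so unchanged cytopenia is given an onset date

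*SAP*

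**What the plan says.** SAP section 10.3 plans three outputs for hematology parameters that have CTCAE grades:

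- A count: "Incidence of subjects with worst post-baseline grade. Each subject will be counted only for the worst grade".
- A comparison with baseline: "Shift tables to compare baseline to the worst post-baseline value using CTCAE grades".
- A timing table: "Summary of time to onset to worst post-baseline grade (defined as the time from treatment start to first occurrence of worst post-baseline grade"). Its inclusion rule reads: "this table will present summary statistics over all grades, but only patients with a worst post-baseline grade will be included".

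The same section derives the worst grade from every available time point, not only from Cycles 1 and 2.

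Baseline is defined in SAP section 7.1: "Thus baseline will be Cycle 1 Day 1 in case there is a value available (not missing) and screening otherwise". The shift table uses it and the timing table does not.

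Two other rules in the plan do refer to worsening. SAP section 10.2 states: "TEAEs are defined as AEs occurring or worsening after the start (date and time) of the first study treatment (any IMP"). Protocol section 8.5 states: "any event will only qualify as a DLT if a worsening of the event from baseline of at least 2 CTCAE Grades occurs".

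**The concern.** Time to onset suggests the time until something new or worse appears. As defined, the variable dates the first appearance of whatever grade turns out to be the subject's worst after baseline, even if the subject already had that grade on Day 1. Those dates go into the same median and quartiles as the dates of subjects who truly worsened.

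Protocol section 7.3 names thrombocytopenia and anemia among the most likely expected effects. A reader of the report may use this table to judge how soon they appear, and a pooled median would then mix treatment effect with pre-existing disease.

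**Working it through.** **1. Can subjects enter with cytopenia?** The entry limits (Protocol sections 8.1 and 8.2.1 to 8.2.3; SAP section 3.2) are:

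| Parameter | Lowest value allowed | Condition |
|---|---|---|
| Hemoglobin | 8 g/dL ("Hemoglobin ≥ 8 g/dL") | all subjects |
| ANC | 1,000/mm³ | all subjects |
| Platelets, without LEN or POM | 50 × 10⁹/L | dose levels of 4 mg/kg and above, with or without DEX; otherwise 80 |
| Platelets, Parts D and E | 30 × 10⁹/L | at least 50% of marrow nucleated cells are plasma cells; otherwise 75 |

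The CTCAE cut-points are not reproduced in the documents, so it is an assumption that values near these limits carry a grade. The two-grade DLT rule and the shift table from baseline grade both presuppose that some subjects start with one.

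**2. Apply the rule literally.**

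| Baseline grade | Worst post-baseline grade | Dated at | Meaning |
|---|---|---|---|
| 0 | 3 | first grade 3 | true worsening |
| 2 | 2 | first post-baseline grade 2, possibly Day 2 | no change |
| 3 | 2 | first post-baseline grade 2 | improvement |

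All three subjects have a worst post-baseline grade, so all three enter the same statistics. The filter might be meant to drop subjects whose worst grade is 0, but the second and third rows would remain. It cannot safely be read as *worsened*, because the incidence bullet uses the same phrase for a count that ignores baseline.

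**3. How early is an unchanged subject dated?** Hematology samples after Day 1 in Cycles 1 and 2 fall on Days 2, 4, 8, 15, 22, 29, 36, 43 and 50 (Protocol section 7.1, Tables 1 and 2). Assume that the baseline grade shows at each sample independently with probability s. Given that it shows at least once, the first occurrence is on Day 2 with probability s / (1 − (1 − s)⁹):

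- s = 1.0: 1.000
- s = 0.8: 0.800
- s = 0.5: 0.5 / (1 − 0.0020) = 0.501
- s = 0.3: 0.3 / (1 − 0.0404) = 0.313

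**4. How often would a subject only improve?** The baseline grade would have to be absent from all nine samples. Under the same model the chance is (1 − s)⁹: 4.0% at s = 0.3, 0.2% at s = 0.5 and practically zero at s = 0.8. Later samples would lower it further.

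**5. Effect on the median.** The plan gives no figure to reproduce, and neither the share of non-worseners nor the true timing is known. For illustration, take the minimum recommended-dose group of 9 (SAP section 5). Worseners are uniform on the stated sample days, and non-worseners follow step 3. Entries are the mean reported median minus the mean median among worseners only, in days, from 200,000 replicates. Each range runs over s = 1.0, 0.8, 0.5 and 0.3. A repeat run agreed within 0.03 day.

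| Worst grade in worseners first reached on | 1 non-worsener of 9 | 2 of 9 | 3 of 9 |
|---|---|---|---|
| Days 2 to 8 | −0.51 to +0.04 | −1.03 to +0.15 | −1.64 to +0.20 |
| Days 2 to 50 | −3.38 to −2.14 | −7.31 to −4.30 | −11.91 to −6.60 |
| Days 22 to 50 | −1.94 to −1.70 | −4.39 to −3.75 | −7.47 to −6.18 |

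Sampling after Day 50 and the larger by-part tables are not modelled.

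**The case against.** The SAP names its variable and defines it in the same sentence. It never claims to measure new or worse cytopenia, and time to worst grade regardless of baseline is a legitimate description. The TEAE and DLT rules define events and set no standard for a laboratory table. This stands in part: the definition is clear, but the word *onset* invites the other reading, and pooling unchanged with worsened subjects makes the statistic hard to interpret under either label.

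Other outputs also cover much of the clinical question. The shift table shows who worsened. SAP section 10.2 summarises time to first hematological TEAE of grade 3 or above, under a rule that includes worsening. By-time-point tables and listings carry dates. None of these replaces the table. The shift table has no timing, the TEAE summary omits grades 1 and 2 and depends on AE reporting, and listings give no summary statistic.

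The day shifts are products of assumption, and their sign is not fixed. That is correct, and they serve only as a range. For thrombocytopenia, the animal data in Protocol section 7.3 point to onset with the first dose, which favours the small end.

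The planned table descriptions are blacked out and may hold a clarifying footnote. That cannot be excluded.

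**Conclusion.** The point holds as a cheap improvement of minor severity. As written, subjects whose pre-existing cytopenia stays at the baseline grade receive an onset date, possibly Day 2, and are pooled with true worseners. No readable part of either document adds a comparison with baseline.

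The size cannot be computed from the documents. The illustrative shifts depend on the assumed number of non-worseners, the persistence s and the onset days; shifts of a week or more arise only with 2 or 3 non-worseners of 9 and onsets that are spread out or late.

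A reader might infer three stronger things that the documents do not support:

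- **That dose decisions or primary results are affected.** The table is descriptive; DLTs, the MTD and every endpoint are derived elsewhere.
- **That improving subjects distort the table materially.** The rule does admit them, but step 4 shows that they should be rare.
- **That the reported median is necessarily much too early.** With early true onsets the shift is near zero and can be slightly late.

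**What to change.** Keep the quantity, name it accurately and add the condition. Suggested wording for SAP section 10.3: *Time to worst post-baseline grade: days from treatment start to first occurrence of the worst post-baseline CTCAE grade, among subjects whose worst post-baseline grade exceeds their baseline grade.* Beside it, show the number who worsened over the number with a baseline and at least one post-baseline value.

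Do not call this time to onset of worsening. A subject at grade 0 who reaches grade 1 on Day 4 and grade 3 on Day 43 would be dated Day 43, although worsening began on Day 4. That label would require dating at the first grade above baseline. Leave the incidence and shift tables as they are.

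The cost is one sentence and one reprogrammed table, with no new data. SAP section 4.3 plans to re-run all analyses at follow-up, so the change would carry through. The downside is fewer subjects per row, in groups that may hold only 9, and a population that differs from the incidence table; the displayed counts make both visible.

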¹ A follow-up visit will be repeated every fourth week (± 2 days) until progressive disease, or receipt of new anti-myeloma treatment, or until death, but no longer than 3 years from the first study drug administration. Follow-up visits may be delayed for a maximum of 2 weeks after the normal visit window due to other reasons (e.g., logistical).

² The EOS visit will occur after at least 28 days after last study drug administration but should be performed before any new MM therapy starts, whichever occurs first. Subjects who complete Cycle 2 but do not receive additional cycles (Cycle 3+) have to perform Follow-up visit 1 and Follow-up visit 2 before EOS visit.

³ Including disease staging based on Durie-Salmon and International Staging System (ISS) criteria and documentation of immunoglobulin type.

⁴Before study drug administration.

⁵ Each cycle, starting with Cycle 3+: pre-dose at Day 1 (CxD1)

⁶ During Cycle 1, all subjects should be given premedication including an antipyretic (e.g., paracetamol) and a histamine H1 receptor blocker according to the local standard of care. In medically justified cases, the investigator may use other medications (e.g., steroids as per local standard but not exceeding 10 mg prednisolone equivalent), doses and/or formulations if this is documented thoroughly in the eCRF and the source data. If no infusion reaction occurs during Cycle 1, then premedication can be stopped at discretion of the investigator for subsequent treatment cycles. Otherwise, the premedication should be continued for subsequent administrations of MOR03087 as well.

⁷ Emergency Laboratory only to be taken if hematology/serum chemistry is not available prior to study drug administration

⁸ Sample to be taken and evaluated before study drug administration. On Day 1, additional sample (except AST and ALT) to be taken 2 hours after end of infusion.

⁹ β2-microglobulin to be measured at Screening only.

¹⁰ Pharmacokinetic sample to be taken predose and then at 1, 2, 4, 8, 14±2 (optional), 22±2, and 28±2 hours after start of first infusion.

¹¹ Pharmacokinetic sample to be taken predose and 2 hours after start of infusion.

¹² Pharmacokinetic sample during treatment Cycles 3+ to be taken every 2nd study drug administration (CxD15) predose and 2 hours after start of infusion.

¹³ Only if subject had no follow-up visit.

¹⁴ Samples for anti-MOR03087 antibodies will also be used to determine tetanus titer if sufficient quantities of serum are available.

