# 7.3 Risks and Benefits to Subjects

MOR03087 provides a novel mechanism of action that may add to the care of MM patients and complement standard-of-care treatment. Based on the available data from nonclinical studies and experiments as well as literature data on CD38, the sponsor is of the opinion that the potential benefit of MOR03087 outweighs the potential risk.

The most likely expected effects—thrombocytopenia, anemia, and diarrhea—are frequently encountered events in malignant hematologic practice. The identified potential toxicities can be readily monitored and managed, e.g., by platelet and red blood cell transfusion or respective treatment of gastrointestinal symptoms. It is expected that the potential risks will be adequately controlled by the design of this first-in-human study (e.g., by the inclusion and exclusion criteria) and by frequent monitoring of potential side effects throughout the entire study.

Based on the results of the 12-week repeated dose toxicity study in marmoset monkeys, the earliest biological effect of MOR03087 expected on non-tumor cells is thrombocytopenia and – at higher doses – diarrhea. Diarrhea was almost reversible at the end of the recovery period. A dose-dependent, reversible thrombocytopenia occurred with the first dose and remained stable thereafter.

The most common serious adverse reactions in subjects treated with a combination of LEN or POM and DEX are venous thromboembolism and grade 4 neutropenia, grade 3 or 4 thrombocytopenia, and venous thromboembolism (see Summaries of Product Characteristics [SmPCs]). It is considered unlikely that neutropenia would be potentiated in combination with MOR03087, as neutrophils only express low levels of CD38.

Generally, it cannot be excluded that treatment with LEN and POM may have an additive effect on thrombocytopenia when used in combination with MOR03087.

Although the mechanism for thrombocytopenia induced by MOR03087 is unknown, there is no preclinical evidence of thrombosis associated with MOR03087 in the marmoset monkey. In addition, *ex vivo* analysis of human and marmoset thrombocytes did not show any signs of thrombocyte activation and aggregation by MOR03087.

Close and frequent monitoring of hematological parameters, i.e., complete blood cell count including white blood cell count with differential count, platelet count, hemoglobin and hematocrit, is implemented in the clinical trial protocol.

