# 9.1.4.2 POM Dose Modification

Subjects will be evaluated for AEs at each visit with the NCI CTCAE version 4.0 as a guide for the grading. Interruptions and reductions are permitted throughout the study.

Table 6 outlines the dose reduction steps for POM. Instructions for dose interruptions and reductions for POM are outlined in Table 7 (hematologic and non-hematologic toxicities).

Table 6Pomalidomide Dose Reduction Steps by Dose Level

Dose Level (Days 1-21 of 28 days)	POM Dose Reduction (Days 1-21 of Every 28-Day Cycle)
Starting dose	4 mg
Dose Level -1	3 mg
Dose Level -2	2 mg
Dose Level -3	1 mg ¹

POM: pomalidomide

¹ The POM treatment regimen should be discontinued if the subject cannot tolerate the 1 mg dose.

Table 7	Pomalidomide Dose Modification Instructions for Toxicities

Toxicity	POM Dose Modification
Neutropenia ANC < $0.5 \ge 10^{9}$ /L) or Febrile neutropenia (fever $\ge 38.5$ °C and ANC < $1.0 \ge 10^{9}$ /L)	Hold POM dosing and follow hematology weekly. If the subject was not receiving GCSF therapy, GCSF therapy may be started at the discretion of the treating physician. When ANC returns to $\geq 0.5 \ge 10^{9}$ /L, restart POM dosing at one dose level lower. Note: GCSF is prohibited during Cycle 1
Thrombocytopenia (Platelets < 25 x 10 ⁹ /L)	Hold POM dosing and follow hematology weekly. POM dosing may resume at one dose level lower once the platelet count has recovered to $\geq 50,000/\mu$ L.
Other $\geq$ Grade 3 POM-related toxicities	Interrupt POM dosing and restart at one dose level lower when toxicity has resolved to $\leq$ Grade 2 at the physician's discretion

ANC: absolute neutrophil count; GCSF: granulocyte colony-stimulating factor; POM: pomalidomide

To initiate a new cycle of POM, the neutrophil count must be  $\ge 0.5 \ge 10^9/L$  with or without GCSF, the platelet count must be  $\ge 50 \ge 10^9/L$ .

POM should be discontinued if subject is unable to tolerate the lowest dose level. At the discretion of the investigator, the treatment with MOR03087 and dexamethasone may be continued.

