Urine will be collected at the various pre- and post-treatment time points described in the flow charts in Section 7.1. The time of void will be documented on the eCRF. In the case of any abnormal result, a microscopic urine examination should be conducted. For the evaluation of urine M-protein 24-hour urine is required and has to be sent to the central laboratory. If urine was collected as standard of care, it is acceptable to use 24-hour urine samples for which collection started up to 48 hours before the respective visit.

A pregnancy test will be performed for women of childbearing potential at various pre- and posttreatment time points either by urine pregnancy test or  $\beta$ HCG test of a serum sample. The pregnancy test assay should have a minimum sensitivity of 25 IU/mL. On dosing days, the result must be available prior to IMP administration.

Laboratory results should be reviewed in a timely manner (i.e., hematology and chemistry prior to dosing). Emergency laboratory samples should only be taken if hematology and serum chemistry results are not available prior to study drug administration. Judgment of clinical significance should be added on the printout for out of range laboratory values, and the printout should be dated and signed.

Emergency Laboratory instruments for measuring parameters relevant for treatment decisions and for documentation of laboratory AEs have to be adequately qualified. In case of discrepancies between the emergency laboratory and principal local laboratory values, the emergency laboratory value should be the relevant value if the emergency laboratory value was used to decide on treatment (administration, continuation or interruption). Further, laboratory AEs should be followed up by the instrument with which the laboratory AE was first reported.

If an abnormal laboratory value of grade 4 or an abnormal laboratory value judged to be clinically significant is not reported as an AE, then the investigator should clearly document the rationale for not doing so in the source documentation.

Any abnormal laboratory findings that constitute an AE should be reported as such and should be followed up until the outcome is known. Also, additional diagnostic tests may be indicated to determine a more precise diagnosis of the subject's condition (e.g., ordering a WBC differential count to help characterize a high or low WBC count, or ordering a determination of RBC indices to help characterize a low hematocrit).

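### SAP 10.3 confines unscheduled and emergency-laboratory results to listings without exempting the hematology worst-grade tables, so laboratory-derived grade 3–4 cytopenias can be under-counted

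*SAP*

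**What the plan says.** SAP 10.3 (Clinical Laboratory Evaluations) plans three hematology outputs based on CTCAE grade: incidence by worst post-baseline grade, a shift from baseline to worst grade, and time to first occurrence of the worst grade. Parameters without CTCAE grades get a low/normal/high shift to the worst assessment.

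Two later statements in the same section decide which values feed these tables.

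- The first opens with "Results of unscheduled laboratory evaluations, laboratory data of the emergency laboratory" and ends "screening serology results will only be included in listings". It makes no exception for hematology.
- The second says that laboratory summaries other than the hematology worst-value tables "will only include time points of Cycle 1+2 and EOS visit", and that for the hematology tables "all available time points will be included when deriving worst assessment/worst grade".

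The protocol bears on this in three places.

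- Sections 9.1.4.1 and 9.1.4.2 require weekly hematology while lenalidomide or pomalidomide is stopped for cytopenia. The pomalidomide table reads "Hold POM dosing and follow hematology weekly".
- Section 11.3.4 says that, when laboratories disagree, "the emergency laboratory value should be the relevant value if the emergency laboratory value was used to decide on treatment".
- Sections 15.7.3, 15.11 and 15.12 plan the CTCAE frequency and shift tables without a listings-only rule. They also call for all data to enter the tables where appropriate and for all available safety data from dosed subjects to be used.

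**The concern.** The listings-only sentence and the all-time-points sentence cover the same hematology data, and neither is ranked above the other. The second is written as the exception to the Cycle 1, Cycle 2 and EOS limit, not as an exception to the listings-only rule. The reading that honours both sentences therefore takes worst grade from scheduled visits in all cycles and ignores off-schedule values. A second programmer could fairly read all time points as every value. The two would produce different tables.

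The omitted values are not a random subset. Unscheduled blood counts tend to be drawn because a count is low or a subject is unwell. Laboratory-derived worst grade is also the safety output that does not depend on an investigator deciding whether a value is clinically significant. Laboratory change and clinically relevant abnormal values are secondary endpoint 7.

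**Working it through.** **1. Direction.** Let S be a subject's scheduled post-baseline values and A all post-baseline values, so S is contained in A. The maximum grade over S cannot exceed the maximum over A. The number of subjects with worst grade 3–4 under listings-only is therefore at most the number using all values. Time to worst grade has no fixed direction. It lengthens if the same worst grade is first reached off schedule, and it can move either way if the tabulated worst grade itself is lower.

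**2. Which values are exposed.**

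- *Unscheduled draws (main source).* Protocol Table 2 and section 7.1 put 8c, 8d and 8e on Days 1 and 15 from Cycle 4. A weekly count during a lenalidomide or pomalidomide hold falls on Days 1, 8, 15 and 22, so 2 of 4 counts (Days 8 and 22) are off schedule. Cohort 8c receives neither drug, which leaves 8d and 8e. In Cycles 1–3 hematology is already scheduled weekly in Parts B–E.
- *Emergency laboratory (smaller source).* Table 11 lists hemoglobin, WBC and platelets but no differential, so there is no neutrophil count to lose. It describes the sample as shared with routine chemistry and hematology, and section 11.3.4 limits its use to occasions when routine results are not ready before dosing. Most values therefore duplicate routine ones. The exceptions are results that disagree with the routine laboratory, and the Day 1 sample: "On Day 1, additional sample (except AST and ALT) to be taken 2 hours after end of infusion".

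**3. The plan's own figure.** Protocol 15.9 says that with 9 subjects an AE with a 17% rate is seen at least once with probability 81%, and one with a 23% rate with probability 90%. From 1 − (1 − p)^9:

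- p = 0.17: 1 − 0.83^9 = 0.813
- p = 0.23: 1 − 0.77^9 = 0.905

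Both reproduce. That statement concerns AEs and is used here only as a yardstick.

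**4. Illustration of size.** The documents give no figure for the loss. Assume that a share m of subjects with a true grade 3–4 laboratory value have it only in an unscheduled or emergency result. The tabulated rate is then p(1 − m). With n = 9:

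| True rate p | m | Tabulated rate | Expected subjects of 9 | P(at least one) |
|---|---|---|---|---|
| 23% | 0 | 23.0% | 2.07 | 0.905 |
| 23% | 10% | 20.7% | 1.86 | 0.876 |
| 23% | 25% | 17.3% | 1.55 | 0.818 |
| 23% | 50% | 11.5% | 1.04 | 0.667 |
| 17% | 25% | 12.8% | 1.15 | 0.707 |
| 17% | 50% | 8.5% | 0.77 | 0.550 |

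At p = 23% and m = 25% the expected shortfall is 2.07 − 1.55 = 0.52 subjects. If the all-time-points sentence overrides the listings-only rule, the shortfall is zero for every m.

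**The case against.** The strongest reply is that the sentence on all time points is the specific rule for these tables and so overrides the general one. On that reading nothing is lost. This shows that a loss is not certain. It does not settle the text, because that sentence is framed against a visit limit and says nothing about unscheduled or emergency data.

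Several further points stand and narrow the concern.

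- The weekly counts start only after a low value has been found. If that value was scheduled, it is already in the table. What can be lost is a deeper nadir during follow-up, or an episode whose first low value was itself off schedule.
- A reader might try to size the loss by comparing the chance that 14-day and 7-day sampling each catch a short episode. That models first detection, which is not what follow-up counts do. It has no bearing on Part A, where lenalidomide and pomalidomide are not part of the regimen.
- A reader might infer that losing the 2-hour Day 1 sample hides an early platelet fall. Protocol 7.3 reports that in marmosets a dose-dependent "thrombocytopenia occurred with the first dose and remained stable thereafter". A lasting effect of that kind would appear in the scheduled Day 2 and Day 4 hematology.
- A reader might infer that the primary safety endpoints are biased. Protocol 11.3.1 makes clinically significant laboratory values AEs, and section 8.5 makes laboratory DLTs AEs. SAP 10.2 tabulates TEAEs of grade 3 or higher, with laboratory and blood-disorder terms merged. Those outputs do not pass through the listings-only rule.

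The AE tables are not a full substitute, however. A laboratory value becomes an AE only on investigator judgement, and section 11.3.4 allows even a grade 4 value to go unreported as an AE if the rationale is documented. Section 11.3.4 governs which value is relevant to treatment and AE follow-up, not tabulation, but it shows that the protocol expects the two laboratories to disagree at times.

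**Conclusion.** The concern holds as a conditional one. SAP 10.3 contains two unreconciled rules. If listings-only governs, the laboratory-derived worst-grade incidence and shift tables can under-count grade 3–4 cytopenias, and time to worst grade can be displaced. The documents do not support saying that cytopenias will be under-counted. The error in the counts can only run low. Its size depends on m, which the documents do not give: none if m = 0 or if the broad reading applies, and a quarter of affected subjects if m = 25%. Exposure comes mainly from unscheduled draws in 8d and 8e from Cycle 4, and less from emergency-laboratory platelet, hemoglobin and WBC values. The AE and DLT primary endpoints are not directly affected, and the omitted values remain visible in listings. It should be corrected before the tables are programmed, but it falls below a must-fix.

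**What to change.** Amend SAP 10.3 to say three things.

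1. By-visit laboratory summaries use scheduled values only.
2. Hematology worst post-baseline grade or assessment, the shift tables, and time to worst grade use every post-baseline value: scheduled, unscheduled and emergency laboratory.
3. Where routine and emergency results conflict, the value used is chosen consistently with Protocol 11.3.4.

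The listings-only sentence should then carry an explicit exception for item 2. A separate row for the Day 1 post-infusion sample is optional and not part of the correction.

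The cost is wording and programming. SAP 10.3 already lists these results, so no new data are needed. Reported grade 3–4 laboratory rates may rise. SAP 4.3 re-runs all analyses at long-term follow-up, so one amendment serves both reports.
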